PFS	Progression Free Survival
PK	Pharmacokinetic(s)
PO	Per os (administered by mouth)
PR	Partial response
PT	Prothrombin time
PTT	Partial thromboplastin time
QC	Quality control
RBC	Red blood cell
QD	Once daily
QTc	QT interval corrected
QTcF	QT interval corrected using Fredericia equation
SAE	Serious adverse event
SD	Standard deviation or stable disease
T _{1/2}	Terminal elimination half-life
T ₃	Triiodothyronine
T ₄	Thyroxine

Abbreviation or Term¹	Definition/Explanation
T _{max}	Time of maximum observed concentration
TID	Three times daily
TSH	Thyroid-stimulating hormone
ULN	Upper limit of normal
ULQ	Upper limit of quantitation
UV	Ultraviolet
WBC	White blood cell
WOCBP	Women of childbearing potential
WONCBP	Women of nonchildbearing potential

All of these abbreviations may or may not be used in protocol.

PROTOCOL SIGNATURE

I confirm that I have read this protocol, and I will conduct the study as outlined herein and according to the ethical principles stated in the latest version of the Declaration of Helsinki, the applicable ICH guidelines for good clinical practice, and the applicable laws and regulations of the federal government. I will promptly submit the protocol to the IRB for review and approval. Once the protocol has been approved by the IRB, I understand that any modifications made during the course of the study must first be approved by the IRB prior to implementation except when such modification is made to remove an immediate hazard to the subject.

I will provide copies of the protocol and all pertinent information to all individuals responsible to me who assist in the conduct of this study. I will discuss this material with them to ensure that they are fully informed regarding the study treatment, the conduct of the study, and the obligations of confidentiality.

Note: This document is signed electronically through submission and approval by the Principal Investigator in the University of Utah IRB Electronic Research Integrity and Compliance Administration (ERICA) system.

STUDY SUMMARY

Title	A Phase 2 study of Radium-223 and Radiotherapy in Hormone-Naïve Men with Oligometastatic Prostate Cancer to bone
Short Title	Radium-223 and Radiotherapy for Oligometastatic Prostate cancer (RROPE)
Protocol Number	IRB #102312
IND	IND Exempt
Phase	Phase IIA
Design	Prospective, single arm, non-randomized, non-blinded open label study of Radium-223 and radiotherapy in men with oligometastatic prostate cancer to bone
Study Duration	3-4 years (accrual at 2 patients per month. Study duration 6 months per patient. 2 year follow up.)
Study Center(s)	This is a single site study conducted at the Huntsman Cancer Institute
Objectives	Primary Objective: Freedom from Androgen Deprivation Therapy (ADT) or other antineoplastic systemic at 15 months. Secondary Objective: QOL assessments, Progression Free Survival, Overall Survival
Number of Subjects	20
Diagnosis and Main Eligibility Criteria	Men with Prostate Cancer and no more than 5 sites of bony metastatic disease without visceral involvement.
Study Product, Dose, Route, Regimen	
 Radium-223 55 kBq (1.49 mCi)/kg (+/- 10% total dose) at study enrollment, and then every 4 weeks following definitive radiation therapy for a total of six Radium-223 infusions. Hypofractionated Radiotherapy to all oligometastatic sites
Duration of administration	6 months of therapy
Reference therapy	Institutional Care Standard (99% of subjects starting Androgen Deprivation Therapy by 15 months)

Statistical Methodology	Assess the proportion of ADT naïve men who progress and require ADT at 15 months.
-------------------------	-----------------------------------------------------------------------------------

1 OBJECTIVES

We hypothesize that treatment with Radium-223 and focal radiotherapy to 5 or fewer sites of clinically detectable bony metastases will delay the time to start systemic therapies (androgen deprivation therapies (ADT) or other antineoplastic systemic therapies). This hypothesis will be tested through the following aims.

1.1 Primary Objectives and Endpoint

1.1.1 Determine if 20% of ADT naïve men treated with concurrent EBRT and Radium-223 will not require ADT for progression by 15 months.
Endpoint: Determine the time from start of study therapy to start of ADT.

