showed a further improvement in overall survival to 3.6 months with a hazard ratio of 0.695 (i.e., 30.5% reduction in risk of death) [9]. Moreover, the toxicity profile appeared excellent with grades 3-4 neutropenia in 1.8% and thrombocytopenia in 4% of patients. Reassuringly, long-term, 24-month outcomes in the previous randomized phase II trial showed no increase in hematologic toxicities [6, 7].

Radiotherapy for Oligometastasis: In 1995, Hellman and Weichselbaum coined the term “oligometastases” to characterize a state of limited metastasis in which aggressive local control measures could be potentially curative [10, 11]. This led to the development of prospective clinical trials employing the use of Stereotactic Body Radiotherapy (SBRT) to ablate visible oligometastatic disease with curative intent [12]. This approach has been demonstrated to be safe and effective, with local control rates in the 80% range, and durable progression-free survival rates around 20%. In one of the only trials evaluating the role of SBRT exclusively in 40 patients with bone only metastatic prostate cancer, the actuarial 24-month local tumor control rate was 95.5% as measured by MRI and PET CT imaging and the median initial PSA before treatment was 5.4 ng/dl which dropped to 2.7 ng/dl after 3 months [13]. We propose that the combination of external beam radiotherapy and Radium-223 will be an effective therapy at controlling oligometastatic prostate cancer in hormone-therapy naïve patients.

Comparator Cohort:

At the Huntsman Cancer Institute at the University of Utah, 100% of persons have been started on systemic therapies to treat their metastatic prostate cancer by 15 months of the identification of oligometastasis. The goal of the current study is to assess whether the Radium-223 and EBRT to oligometastatic sites will delay the need to initiate additional antineoplastic systemic therapies by 15 months.

Other Comparators of interest that are not specified as the primary aim:

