10.1 Primary Endpoint – 15 month Hormone Free Survival

The primary objective is to determine the hormone-therapy-free survival time for men treated with sequential EBRT and Radium-223 and determine whether it is a 20% risk reduction over the institutional comparator of 100% use of systemic therapy by 15 months. The primary outcome is 15 months hormone-free survival. Patients will remain on study treatment for the duration defined by the calendar or for disease progression. Patients will be followed up to determine the start of ADT which will be used to measure the primary end point.

For the purposes of this study, progression will be measured after the completion of EBRT and the delivery of Cycle 2 of Radium-223 and defined as either:

Biochemical Progression:

- For those subjects whose PSA is greater than 20ng/ml at baseline who do not have any PSA decrease after starting therapy: biochemical progression will be defined as a 10% rise over the baseline.

- For those subjects whose PSA is greater than 20ng/ml at baseline, who demonstrate decrease in PSA after study treatment: if the PSA nadir remains > 20ng/ml, biochemical progression will be defined as a PSA rise greater than 10% of the PSA nadir. If the PSA nadir is < 20ng/ml, biochemical progression will be defined as a PSA rise greater than 10% of the PSA nadir.

-For those subjects whose PSA is less than 20ng/ml at baseline: biochemical progression will be defined as PSA >20ng/ml and 10%.

*Any PSA test that would meet a failure definition has to be validated through Huntsman Cancer Institute or a Veterans Affairs Hospital with a repeat PSA test no sooner than 5 days and no later than 14 days from the initial notification of the result demonstrating progression.

OR

Radiographic progression: Any new, progressing, or reappearing lesion on Bone Scan, CT/Scan, or MRI compared to the same scan performed previously. Radiographic Progression will be determined by Prostate Cancer Clinical Trials Working Group (PCWG2) and RECIST 1.1 as described below (section 10.1.1).

* Of note: For a patient to meet radiographic progression criterion for appearance of new bone lesion only, the patient must demonstrate appearance of new bone disease, as confirmed by the treating radiation oncologist, and also meet the biochemical progression definition set out above.

OR

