11 STATISTICAL CONSIDERATIONS

The primary objective is to determine the hormone-therapy-free survival time for men treated with concurrent EBRT and Radium-223 and determine whether 20% of subjects do not meet the progression endpoint and require ADT at 15 months. The primary outcome is 15 months hormone- (or other systemic) therapy-free survival. The null hypothesis is that 99% of subjects will start systemic therapy within 15 months. The alternative hypothesis is that 80% of subjects will start systemic therapy within 15 months. With 20 evaluable subjects there will be 93% power for this alternative hypothesis using an exact binomial test at the one-sided 0.05 significance level. The null hypothesis will be rejected if 2 or more out of 20 subjects are not placed on systemic therapy within one year.

One of the secondary endpoints is to determine the hormone-therapy-free survival time for men treated with concurrent EBRT and Radium-223 and determine whether it is a 30% risk reduction over the SWOG intermittent ADT historic cohort. This secondary hypothesis will be tested only if the primary null hypothesis is rejected. The outcome for

this secondary hypothesis is 15 month hormone- (or other systemic) therapy-free survival. In 2012 a SWOG cooperative group trial reported that 78% of subjects on intermittent androgen therapy had resumed ADT within 15 months, and this proportion will be used as a null hypothesis. With 20 evaluable subjects, and a null hypothesis that 78% or more of patients will start systemic therapy within 15 months there will be 80% power to detect an alternative hypothesis that 48% or fewer will start systemic therapy within 15 month using an exact binomial test at one-sided alpha =0.05 significance level.

Additional, secondary endpoints are time to first skeletal related event (SRE), overall survival, PSA doubling time, overall survival and toxicities. All secondary endpoints will be evaluated descriptively. Time to first SRE, OS, and PSA doubling time will be analyzed via Kaplan-Meier product limit methods and associated 95% confidence intervals. Toxicities will be tabulated using CTAE version 4.0. The number and proportion of subjects with toxicities will be reported.

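### The primary event is start of ADT in some places and start of any systemic therapy in others, and nothing in the plan says which one governs

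*Combined protocol and SAP*

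**What the plan says.** The narrow definition, ADT only, appears in these places:

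- Section 1.1.1: the objective is that 20% of men "will not require ADT for progression by 15 months", and the endpoint is "Determine the time from start of study therapy to start of ADT".
- Section 10.1, measurement sentence: "Patients will be followed up to determine the start of ADT which will be used to measure the primary end point".
- Study Summary: the reference therapy row gives 99% of subjects starting ADT by 15 months, and the statistical methodology row refers to men who progress and need ADT.
- Section 11, opening sentence: "determine whether 20% of subjects do not meet the progression endpoint and require ADT at 15 months".

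The broad definition, ADT or other systemic therapy, appears in these:

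- Study Summary, primary objective: "Freedom from Androgen Deprivation Therapy (ADT) or other antineoplastic systemic at 15 months".
- Section 1, hypothesis: delay in starting systemic therapies, spelled out as ADT or other antineoplastic agents.
- Section 2, institutional comparator: "100% of persons have been started on systemic therapies" by 15 months. Section 10.1 repeats the comparator as 100% use of systemic therapy.
- Section 11: "The primary outcome is 15 months hormone- (or other systemic) therapy-free survival". The null (99%), the alternative (80%) and the rejection rule are all worded for systemic therapy.

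The first secondary objective has the same split. Section 1.2.1 measures start of ADT, Section 11 uses the broad outcome, and the 78% SWOG benchmark counts men who resumed ADT.

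**The concern.** The two definitions disagree about one kind of patient: the man who by 15 months has started a systemic agent other than ADT and has had no ADT. Sections 1.1.1 and 10.1 count him as a success. Section 11 counts him as a failure.

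Such a man can occur. Section 7.3 bars other anti-cancer therapy alongside study treatment, but treatment lasts about six months. Section 7.4 keeps men who progress in follow-up, and Section 8.1.1 expects chemotherapy or investigational drugs, if needed, to be deferred to that period. The months between the end of treatment and month 15 are therefore open to non-ADT therapy.

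The trial succeeds on 2 of 20, so very few men need to be scored differently to change the conclusion. Section 11 also tests the SWOG comparison only if the primary null is rejected, so a false primary success would open that test too. If the definition is chosen after outcomes are known, it can be chosen by result.

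**Working it through.** **Inputs.** From Section 11: 20 evaluable subjects, null 99% starting systemic therapy (1% free), alternative 80% (20% free), one-sided 0.05 exact binomial test, reject if 2 or more are free. The hypotheses' 15-month horizon is used throughout.

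**Step 1: reproduce the plan's figure.** With X the number counted as free and p the probability of being counted as free,

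P(X ≥ 2) = 1 − (1 − p)^20 − 20p(1 − p)^19.

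- Power, p = 0.20: 1 − 0.01153 − 0.05765 = 0.9308, matching the stated 93%.
- Type I error, p = 0.01: 1 − 0.81791 − 0.16523 = 0.0169.
- A cutoff of 1 would give 1 − 0.81791 = 0.182, so 2 is the right cutoff at the 0.05 level.

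**Step 2: score each type of man at 15 months.**

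| Therapy started by 15 months | ADT-only event | Any-systemic event |
|---|---|---|
| None | success | success |
| ADT, with or without other agents, in any order | failure | failure |
| Non-ADT systemic therapy only | success | failure |

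Only the last row differs. A man who starts another agent first and then ADT before month 15 fails under both definitions.

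**Step 3: effect without any assumed rate.** Two men in the last row meet the 2-of-20 threshold by themselves under ADT-only scoring. One does so together with a single man who is truly free of therapy.

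**Step 4: sensitivity of the false-positive probability.** Take the null as 99% starting any systemic therapy. Let q be the fraction of those men whose only systemic therapy by 15 months is non-ADT. The documents give no value for q. Under ADT-only scoring,

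p = 1 − 0.99(1 − q).

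| q (assumed) | p | (1 − p)^20 | 20p(1 − p)^19 | P(X ≥ 2) |
|---|---|---|---|---|
| 0 | 0.0100 | 0.81791 | 0.16523 | 1.7% |
| 1% | 0.0199 | 0.66897 | 0.27166 | 5.9% |
| 2% | 0.0298 | 0.54604 | 0.33544 | 11.9% |
| 5% | 0.0595 | 0.29321 | 0.37099 | 33.6% |

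At q = 1% the nominal 5% level is already exceeded.

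**Step 5: the other reading of the 99%.** If the institutional figure counts ADT, as the Study Summary words it, ADT-only scoring matches the null and Step 4 does not apply. Everyone who starts ADT has started a systemic therapy, so at least 99% would then start some systemic therapy. Scoring the broad event against a 99% null keeps type I error at or below 1.7%. The broad event is therefore safe under either reading of the benchmark.

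**The case against.** The best defence is that ADT is shorthand. The Section 1 hypothesis names ADT and other antineoplastic agents together and says the aims that follow will test it, and the formal test in Section 11 is written for systemic therapy. An analyst who follows Section 11 keeps the 1.7% type I error. It can be added that the cohort is hormone-naïve, that Section 2 gives immediate ADT as the standard of care, and that Section 7.3 bars other therapy during study treatment, so q may be close to zero.

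Part of this stands. The inflation arises only if scoring departs from Section 11, and no value of q above zero has support in the documents. The shorthand reading is not secure, however. Sections 1, 2 and 11 name ADT and other systemic therapies as separate things, and Section 10.1, the section headed as the primary endpoint, uses "start of ADT which will be used to measure the primary end point".

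Three stronger readings are tempting and are not supported:

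- *That one set of sections contradicts another cleanly.* Both wordings occur within the Study Summary, Section 10.1 and Section 11.
- *That ADT-only scoring certainly favours the trial.* That depends on what the 99% counts. Section 11 words it as systemic therapy and the Study Summary as ADT, and the documents do not show which the institutional data recorded.
- *That every man who starts another agent first is scored differently.* Only men with no ADT at all by month 15 are.

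**Conclusion.** The point holds as an unresolved conflict in the definition of the primary event. It is not an error in the sample-size calculation, which reproduces. A man on non-ADT systemic therapy only at 15 months is both a success and a failure under the current text, and with a cutoff of 2 of 20 one or two such men can reverse the conclusion.

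The size is conditional. If the 99% null counts any systemic therapy, as Section 11 and the comparator text in Sections 2 and 10.1 indicate, and if scoring is by ADT alone, the false-positive probability runs from 1.7% at q = 0 to 33.6% at q = 5%. The values of q are assumptions and may be small in practice. It should be corrected before any outcome is scored.

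**What to change.** State one primary event everywhere: start of ADT or of any other systemic antineoplastic therapy, whichever comes first. The places to change are:

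- the reference therapy and statistical methodology rows of the Study Summary;
- the objective and endpoint in Section 1.1.1;
- the measurement sentence in Section 10.1;
- the opening sentence of Section 11.

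Confirm from the institutional data that the 99% and 100% figures count this same event, and say so beside them.

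In Section 1.2.1 use the same event, to match the secondary outcome in Section 11. Add that the SWOG 78% counts resumption of ADT, so the broader event in this trial is the stricter comparison against that benchmark.

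The cost is a wording amendment in these places and one check of the benchmark data. Sample size (20), cutoff (2), exact type I error (1.7%) and power (93.1%) are unchanged, because Section 11 is already calibrated to systemic therapy. The definition becomes slightly stricter for the trial than ADT alone.

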1.2 Secondary Objectives and Endpoint

1.2.1 Determine the hormone-therapy free survival time for men treated with concurrent EBRT and Radium-223 and determine whether it is a 30% risk reduction over the SWOG intermittent ADT historic cohort
Endpoint: Determine the time from start of study therapy to start of ADT.

1.2.2 Evaluate health-related quality of life (QOL) as scored by the 50-item Expanded Prostate Inventory Composite (EPIC) EPIC urinary, bowel, sexual, and hormonal domains. The PROMIS 29 will be used to assess general function and well-being
Endpoint: The PROMIS 29 will be used to assess general function and well-being.

1.2.3 Evaluate time to first skeletal related event (SRE)
Endpoint: Documentation of complications associated with bone metastases and may include (but not limited to) fractures, spinal cord compression, bone pain, and hypercalcemia.

1.2.4 Evaluate the PSA doubling time
Endpoint: Time elapsed from baseline PSA to double in value.

1.2.5 Evaluate overall survival at 2 years relative to the SWOG intermittent ADT historic cohort.
Endpoint: Patients will be followed for survival for two years after study enrollment

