7.4 Duration of Therapy

Subjects must be withdrawn from the study treatment for the following reasons:

Patients are expected to receive one neo-adjuvant dose of Radium-223 followed by EBRT for 2 to 6 weeks followed by 5 additional cycles of Radium-223. The treatment phase of the study should be completed in approximately 6 months pending dose delay or discontinuation

- Subject withdraws consent from the study treatment and/or study procedures. A subject must be removed from the trial at his/her own request or at the request of his/her legally acceptable representative. At any time during the trial and without giving reasons, a subject may decline to participate further. The subject will not suffer any disadvantage as a result.
- Subject is lost to follow-up.
- Death.
- Disease progression as defined in section 10

- In the event of disease progression, the subject will no longer receive study treatment, but will remain on the study for all follow-up evaluations, which include indicated imaging studies, lab draws, and all questionnaires.

Subjects may be withdrawn from the study for the following reasons:

- The subject is non-compliant with study drug, trial procedures, or both; including the use of anti-cancer therapy not prescribed by the study protocol.
- If, in the investigator's opinion, continuation of the trial would be harmful to the subject's well-being.
- The development of a second cancer.
- Development of an intercurrent illness or situation which would, in the judgment of the investigator, significantly affect assessments of clinical status and trial endpoints.
- Deterioration of ECOG performance status to 4.

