8.1 Dose Modifications

8.1.1 Dose Modification

Every effort should be made to administer the full dosing regimen of Radium Ra-223 dichloride. Adjustment of dose level is not permitted.

Study visits for administration of Radium-223 during the treatment period should occur at 28 day intervals (within a window of 0 and +14 days). Radium-223 cannot be administered earlier than 28 days from the previous administration. Dosing delays may be instituted under the following circumstances:

Disease progression:

The Investigator should delay cytotoxic chemotherapy, other systemic radioisotope, hemibody external radiotherapy or other investigational drug until the follow-up period. If such treatments have to be given during the treatment period, further study drug administrations must be discontinued.

Patients with a single PSA result that meets biochemical progression criteria may continue on treatment, at the investigator's discretion, until a confirmatory PSA result is returned. Upon confirmed biochemical progression study treatment MUST be discontinued.

Patients who demonstrate radiographic or clinical progression must discontinue study treatment.

Myelosuppression:

Treatment-related changes in hematology parameters may occur.

- If a patient experiences CTCAE v4.03 Grade 3 or 4 neutropenia, thrombocytopenia, or anemia the administration of study drug should be delayed until recovery to Grade 2 or better.
- If a patient experiences CTCAE v4.03 Grade 3 or 4 neutropenia, thrombocytopenia, or anemia lasting > 14 days, further study drug administrations must be discontinued.
- Blood transfusion is acceptable between study drug administrations but not prior to the start of the study. Use of biologic response modifiers, such as G-CSF or GM-CSF, is allowed in the management of acute toxicity.

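### PSA doubling time is measured from baseline to twice baseline and analysed by Kaplan-Meier, with no rule for systemic therapy that starts before PSA has doubled

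*Combined protocol and SAP*

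**What the plan says.** - **Definition.** Section 1.2.4 gives the endpoint as "Time elapsed from baseline PSA to double in value".
- **Analysis.** Section 11 states: "Time to first SRE, OS, and PSA doubling time will be analyzed via Kaplan-Meier product limit methods". It also states: "All secondary endpoints will be evaluated descriptively". Its quality-of-life paragraph lists PSA doubling time among the survival outcomes for exploratory logrank tests.
- **Biochemical progression (Section 10.1).** For baseline PSA above 20 ng/mL with no fall, "biochemical progression will be defined as a 10% rise over the baseline". With a fall, the reference becomes the nadir: "If the PSA nadir is < 20ng/ml, biochemical progression will be defined as a PSA rise greater than 10% of the PSA nadir", and the same 10% applies when the nadir stays above 20. For baseline below 20, "biochemical progression will be defined as PSA >20ng/ml and 10" percent, read here as above 20 ng/mL with a rise of at least 10%.
- **Consequence.** Section 8.1.1: "Upon confirmed biochemical progression study treatment MUST be discontinued". Section 7.4 says that men who progress "will remain on the study for all follow-up evaluations, which include indicated imaging studies, lab draws, and all questionnaires".
- **Systemic therapy.** Section 11 takes 99% (null) and 80% (alternative) of men to start systemic therapy within 15 months. Follow-up lasts about two years.
- **Not stated.** No section says whether a man who starts ADT or another systemic agent before doubling is censored, counted as having a competing event, or followed on his on-therapy PSA.

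**The concern.** Systemic therapy disrupts this endpoint, and the trial expects it in most men during follow-up. It is started largely because disease, often PSA, is progressing, and ADT lowers PSA. Kaplan-Meier needs censoring that is unrelated to the time to the event, which is doubtful here. The definition also runs from baseline, so a man whose PSA falls and then regrows must first recover the fall before he counts as doubling.

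At stake is whether the reported figure can be read as PSA kinetics. It could instead reflect baseline PSA, when ADT was started, and depth of response. The exploratory logrank tests would inherit the same mixture.

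**Working it through.** **The plan's own figure.** The plan states no number for PSA doubling time. The 80% and 99% come from the primary test (20 men, reject if 2 or more stay free of systemic therapy), which reproduces:
- type I error: 1 − 0.99^20 − 20 × 0.01 × 0.99^19 = 0.0169;
- power: 1 − 0.80^20 − 20 × 0.20 × 0.80^19 = 0.9308, against 93% stated.

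**Which threshold comes first, with no initial PSA fall.** From Section 10.1, the threshold is 1.10 × baseline above 20 ng/mL. Below 20 it is the larger of 20 and 1.10 × baseline. Doubling is 2.0 × baseline. Under exponential growth, the share of the doubling time used up at the threshold is log2(threshold / baseline).

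| Baseline (ng/mL) | Threshold ÷ baseline | Share of doubling time | First |
|---|---|---|---|
| 30 | 1.10 | 0.14 | progression |
| 15 | 1.33 | 0.42 | progression |
| 12 | 1.67 | 0.74 | progression |
| 10 | 2.00 | 1.00 | tie |
| 8 | 2.50 | 1.32 | doubling |
| 5.4 | 3.70 | 1.89 | doubling |

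**With an initial fall.** Take baseline 30 and nadir 10. Biochemical progression is at 1.1 × 10 = 11 ng/mL, or 0.37 × baseline, while the endpoint waits for 60. The stereotactic radiotherapy series cited in Section 2 had median PSA of 5.4 before treatment and 2.7 after 3 months (printed in ng/dl, read here as ng/mL). Treat these as one man's values with nadir at 3 months. Twice baseline is 10.8 = 4 × 2.7, so he needs two doublings from nadir. With a true doubling time of 4 months, the endpoint reads 3 + 2 × 4 = 11 months, even with no systemic therapy.

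**Size if men are censored at ADT.** This was simulated with 200,000 men per scenario. Assumptions, none from the documents except 5.4 as one of the medians:
- log-normal baseline PSA, log-SD 1.0 (0.8 at median 30);
- median true doubling time 4 or 8 months, log-SD 0.7, independent of baseline;
- no initial fall; ADT 1 month after the threshold; 24 months of follow-up.

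| Median baseline | Baseline above 20 | ADT before doubling (4 / 8 months) | Kaplan-Meier vs true median, 4 months | Same, 8 months |
|---|---|---|---|---|
| 5.4 | 9–10% | 20% / 23% | 4.16 vs 4.00 (+4.0%) | 8.48 vs 8.02 (+5.7%) |
| 10 | 24% | 41% / 45% | 4.38 vs 4.00 (+9.5%) | 9.01 vs 8.02 (+12.3%) |
| 20 | 50% | 66% / 71% | 4.82 vs 4.00 (+20.5%) | 9.95 vs 8.02 (+24.1%) |
| 30 | 69% | 83% / 89% | 5.69 vs 3.99 (+42.6%) | 11.93 vs 8.01 (+48.9%) |

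**Size if on-therapy PSA is used.** In the extreme where ADT suppresses every later doubling, the proportion seen to double by 24 months is 80% against a true 99% (median baseline 5.4, doubling time 4). It is 11% against 94% at median baseline 30 and doubling time 8.

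**The case against.** The strongest defence is that only one narrow item is missing, in a descriptive endpoint in 20 men. Four stronger readings are tempting, and the documents do not support them.

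1. A reader might infer that many men will stop at a 10% rise. That rule covers only men whose baseline PSA is above 20 ng/mL. The trial's baseline distribution is not given, and the only level cited, a median of 5.4 in another series, points to the small end of the bias.
2. A reader might infer that only men with baseline below 10 can ever be seen to double. Crossing the threshold ends study treatment, not PSA follow-up. ADT is not mandated at progression, and follow-up visits are three-monthly with a wide window (+90/−30 days). A man above 10 can therefore double before ADT, or cross both levels between visits.
3. A reader might infer from the 14% share that progression would be declared within weeks. Section 10.1 measures progression only after EBRT and cycle 2, and requires a repeat PSA.
4. A reader might infer that the plan does censor at ADT, or that 80% to 99% of men start therapy before doubling. The plan states no censoring rule, and those percentages refer to 15 months, not to doubling.

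The slope method can also be criticised. In a simulation with baseline 30, PSA halved by month 3, monthly values and therapy straight after confirmed progression, the median fit from the observed nadir had 3 points. With log-PSA noise SD 0.10, a true 8 months read 5.2 and a true 12 read 6.0. With SD 0.05 they read 7.0 and 9.1. This downside stands. It is smaller than the distortion in the stated endpoint, which in the same setting reads 3 + 2 × 8 = 19 and 3 + 2 × 12 = 27 months. It nearly disappears with long series: at baseline 8, a true 8 read 7.9 to 8.0.

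None of this supplies the missing rule, and either natural way of filling the gap within Kaplan-Meier distorts the estimate.

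**Conclusion.** The point holds in this form: the plan gives no rule for systemic therapy before PSA doubling, and its baseline-to-twice-baseline definition does not isolate a doubling time once PSA has first fallen.

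Censoring at therapy would bias the median upward. Using on-therapy PSA would hide or delay doubling. The split at 10 ng/mL is arithmetic from Section 10.1 and assumes no initial fall. The upward direction assumes that therapy is prompted by progression. The +4% to +49% rests on assumed baseline PSA, growth and ADT timing, and describes censoring at ADT only. It is a range of possibilities, not a forecast for this trial.

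The primary test, the sample size and the safety assessment are unaffected. The consequence is confined to one descriptive secondary endpoint and the logrank tests that use it.

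**What to change.** **Preferred.** In Section 1.2.4 and both places in Section 11:
- Define doubling time as ln 2 divided by the slope of ln(PSA) on time, using only values before any ADT or other systemic therapy.
- Fix the start in advance, for example the cycle 2 value or the first value after nadir. Starting at the observed nadir itself selects a low value.
- Require a minimum number of values, for example 3 or more.
- Report the median and quartiles, the number with a non-positive slope, the number not estimable, and the number starting systemic therapy before doubling.
- Remove PSA doubling time from the Kaplan-Meier and logrank outcomes.

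**Alternative, if time to doubling is kept.** Treat systemic therapy as a competing event, report cumulative incidence instead of Kaplan-Meier, and report the number starting therapy before doubling. This describes the chance of an observed doubling before therapy. It still mixes depth of response with regrowth.

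**Cost.** No new data are needed, because the Study Calendar already schedules PSA at every cycle and at follow-up. The definition sits in the protocol objectives, so the change needs an IRB-approved amendment under Section 15.7. Short series will give imprecise slopes that read low, mainly in men with high baseline PSA, and a minimum count will leave some men not estimable. Both should be stated with the result.
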